#### **4. Study Procedures:**

##### Unfractionated heparin group:

Patients in this group will receive UFH anticoagulation as is current standard of care at Children's. During cannulation a bolus dose of 50-100 units/kg of intravenous UFH will be given. A continuous UFH infusion based on age will be initiated once ACT is < 300 seconds. Infants less than one year will receive a starting dose of 28 units/kg/hour and children > 1 year will receive a starting dose of 20 units/kg/hour per current Children's protocol.

The UFH infusion will be titrated based on targeted anti-factor Xa, aPTT, and thromboelastogram. Labs will be drawn per current standard of care as noted below.

##### aPTT and anti-factor Xa levels:

From time of cannulation until goal anticoagulation achieved: every 4-6 hrs

Once achieved goal: every 6 hours

Heparin dose change: 4 hours after change

##### Other labs:

Daily TEG, PT/INR, d-dimer, fibrinogen, antithrombin, triglycerides, plasma free hemoglobin

Every 12 hour complete blood count

Every one hour ACT

##### Bivalirudin group:

Patients in the bivalirudin group will initially receive UFH to allow for time for consent and randomization. During cannulation, an intravenous UFH bolus of 50-100 units/kg will be given. A continuous UFH infusion based on age will be initiated once ACT is < 300 seconds. Infants less than one year will receive a starting dose of 28 units/kg/hour and children > 1 year will receive a starting dose of 20 units/kg/hour. Once consent is obtained, the patients will be immediately transitioned from UFH to bivalirudin. The initial bivalirudin dose will be 0.15mg/kg/hr.

The bivalirudin infusion will be titrated via the nomogram below based on aPTT. Goal aPTT will be 1.5-2.5 times baseline. For patients with a normal aPTT prior to cannulation this translates to aPTT between 60-80 seconds.

Measured aPTT	Bivalirudin dose adjustment
< 45 seconds or < 16 seconds below target aPTT	Increase by 0.04 mg/kg/hr
45-59 seconds or 1-15 seconds below target aPTT	Increase by 0.02 mg/kg/hr
60-80 seconds or 1.5-2.5 times baseline aPTT	No change
81-95 seconds or 1-15 seconds above target aPTT	Decrease by 0.02 mg/kg/hr
>95 seconds or > 16 seconds above target aPTT	Decrease by 0.04 mg/kg/hr

For patients with renal insufficiency or failure, the initial bivalirudin dose will be adjusted based on creatinine clearance according to the nomogram below.

Creatinine Clearance (CrCl)	Initial infusion rate
> 60 ml/minute	0.15 mg/kg/hr
30-60 ml/minute	0.08 mg/kg/hr
< 30 ml/minute	0.05 mg/kg/hr
Dialysis dependent	0.02mg/kg/hr

aPTT labs:

From time of cannulation until goal anticoagulation achieved: every 2 hours

Once achieved goal: every 6 hours

Bivalirudin dose change: 2 hours after change

Other labs:

Daily TEG, PT/INR, d-dimer, fibrinogen, antithrombin, triglycerides, plasma free hemoglobin

Every 12 hour complete blood count

Every hour ACT

Blood product transfusion:

For both arms of the study patients, transfusion parameters will include: 15 ml/kg (maximum of 1 unit) of platelets for platelet count < 100 x 10^9, 1 unit/kg of cryoprecipitate for fibrinogen < 100 mg/dL, and 15 ml/kg (maximum of 1 unit) of packed red blood cells for hemoglobin < 8 -10 g/dL.

Cross over:

Patients in the UFH arm may cross over into the bivalirudin arm if they develop heparin induced thrombocytopenia or heparin resistance defined as UFH dose of > 70 u/kg/hour with inability to obtain goal Xa or aPTT. Bivalirudin patients may cross over into the UFH arm if they are unable to achieve adequate anticoagulation and have continued development of thrombosis in the circuit or the patient or if the patient develops an intracardiac thrombus.

Randomization:

Patients will be randomized 50/50 into the bivalirudin group or the heparin group. Each group will have 15 patients for a total of 30 patients. Randomization will occur via a sealed envelope assignment.

Research related costs:

Version 1.3 13JUN2018

Thrombin generation assay will be performed on day one and on day three for patients in both arms. The patients will not be responsible for the cost of the test. In addition, per current standard of care at Children's echocardiograms will be performed at time of cannulation and as needed to evaluate cardiac function and/or cannula position. If an echocardiogram is performed on patients in the bivalirudin arm to evaluate for intracardiac thrombus, the patient will not be responsible for the charge.

Patients will be responsible for all standard ECMO related costs including blood product transfusion and anticoagulant. The average wholesale price of bivalirudin for a 250mg vial is \$609. On average one vial per day will be used per patient. The average wholesale price of unfractionated heparin for a 250ml bag is \$20. The entire bag or portion of bag will be used per day per each patient. Therefore, the patients in the bivalirudin arm may incur a higher cost.

Data will be collected on the patients from time of ECMO cannulation to time of hospital discharge. Blood draws for the both groups of patients will follow current CMC protocol for ECMO except that bivalirudin patients will not get anti-factor Xa testing. The only additional test will be a thrombin generation assays. Thrombin generation assays will require an extra 5.4 ml total of blood. In addition, blood samples for dilute thrombin time, ecarin chromogenic assay, bivalirudin level and aPTT will be frozen and stored for future analysis after study completion. Samples will be drawn daily, and obtained from leftover SOC coagulation labs drawn per protocol so no additional blood sampling will be required. Patients will not be responsible for the cost of this analysis.

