**2. Background:**

Extracorporeal membrane oxygenation (ECMO) is a lifesaving therapy for patients with respiratory and/or cardiac failure. Approximately 1500 to 2000 neonatal and pediatric patients are placed onto extracorporeal membrane oxygenation (ECMO) each year for respiratory failure [8]. At Children's Medical Center, we place approximately 40 neonatal and pediatric patients onto ECMO each year. Despite advancements in ECMO circuit technology such as heparin coated tubing, smaller oxygenators, and improved cannula, hemorrhage and thrombosis are the most common complications during ECMO [8, 9]. Approximately 4-11% of neonatal and pediatric ECMO patients suffer an intracranial hemorrhage and 30% have some form of thrombosis [10, 11]. Hemostatic complications during ECMO are associated

with increased morbidity and mortality [5, 11]. In order to prevent catastrophic circuit clotting, anticoagulation is essential.

As mentioned previously, UFH is currently the standard anticoagulant for ECMO but it has several important limitations. UFH requires antithrombin for maximum therapeutic effect but neonates and critically ill patients are known to be deficient in antithrombin. Besides binding to antithrombin, UFH binds to the ECMO circuit and other plasma proteins altering its pharmacokinetics. The tests used to monitor UFH's clinical effectiveness such as aPTT, ACT and anti-factor Xa are all imperfect tests and have been shown to have variable correlation to themselves and to UFH during ECMO [12-16]. There are no randomized studies that have investigated superiority of UFH over other anticoagulants during ECMO. In addition, there is no universally accepted test or combination of tests to monitor the functional effect of UFH during ECMO.

Bivalirudin is a specific and reversible direct thrombin inhibitor. Bivalirudin binds to both bound free and clot-bound thrombin and unlike UFH it does not require antithrombin. In addition, bivalirudin also has a short half-life of 25 minutes and has low to negligible immunogenic potential. Bivalirudin is currently FDA approved for patients with unstable angina undergoing percutaneous transluminal coronary angioplasty (PTCA), percutaneous coronary intervention (PCI) with use of glycoprotein IIb/IIIa inhibitor, and patients with heparin induced thrombocytopenia undergoing PCI [17]. Bivalirudin is currently used off label for pediatrics.

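### The bivalirudin titration table has a probable sign error in row 1, and it does not say that only one of its two aPTT windows applies to a given patient

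*Combined protocol and SAP*

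**What the plan says.** Section 4, bivalirudin group, sets the target just above the table: "Goal aPTT will be 1.5-2.5 times baseline. For patients with a normal aPTT prior to cannulation this translates to aPTT between 60-80 seconds". The five rows of the table are:

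- Row 1, increase by 0.04 mg/kg/hr: "< 45 seconds or < 16 seconds below target aPTT"
- Row 2, increase by 0.02: "45-59 seconds or 1-15 seconds below target aPTT"
- Row 3, no change: "60-80 seconds or 1.5-2.5 times baseline aPTT"
- Row 4, decrease by 0.02: "81-95 seconds or 1-15 seconds above target aPTT"
- Row 5, decrease by 0.04: ">95 seconds or > 16 seconds above target aPTT"

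The protocol does not define a normal aPTT. It does not say which limb prevails when the two disagree. Section 1 makes the percentage of time at goal anticoagulation the primary outcome, and section 14 lists time in the aPTT goal range without naming the range.

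**The concern.** The table is the dosing rule for the study drug, so each aPTT should lead to one instruction. Two separate features prevent that.

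First, the relative limb of row 1 points the wrong way. Read plainly, it gives the larger increase to patients just below target and leaves out those furthest below.

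Second, rows 1 to 5 offer two windows that are not equivalent, joined by *or*. If both are applied to the same patient, one measurement can call for two different actions. It can also count as at goal and off goal, which reaches the primary outcome. The number of dose changes (section 14) and the median bivalirudin dose (section 1) are outcomes too, and both depend on how the table is applied.

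**Working it through.** **Inputs.** The row limits, dose steps, starting rates and goal come from section 4. The documents give no baseline aPTT values, so the baselines of 32, 36, 40 and 50 s are assumptions. *Below target* is taken as below the lower goal limit, and *above target* as above the upper limit. Values are whole seconds.

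**Step 1: the plan's own equivalence.** The plan equates 1.5-2.5 times baseline with 60-80 s. Solving each end for baseline b:

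- 1.5 × b = 60 gives b = 40 s
- 2.5 × b = 80 gives b = 32 s

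No single baseline satisfies both, so the equivalence cannot be reproduced. The range 60-80 s is what the ratio goals for baselines of 32 to 40 s have in common (48-80 s at 32; 60-100 s at 40).

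**Step 2: row 1 against row 2, relative limbs.** Row 1 as printed covers shortfalls under 16 s, and row 2 covers 1-15 s. All 15 whole-second shortfalls match both rows, with +0.04 and +0.02. Shortfalls of 16 s or more match neither. The seconds limb shows the likely intent: 44 s is 60 − 44 = 16 s below target and falls in row 1.

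**Step 3: who is affected when the *or* is kept.** The seconds limb of row 1 catches everything under 45 s. Row 1 therefore misses a far-below value only if that value is at least 45 s and also at least 16 s below 1.5 × b:

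- 1.5 × b − 16 ≥ 45, so b ≥ 61/1.5 = 40.7 s

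At b = 50 s the goal is 75-125 s. Values of 45-59 s are 75 − 45 = 30 down to 75 − 59 = 16 s below target. They miss row 1 and get only +0.02, from the seconds limb of row 2. Such patients can be enrolled, because section 7 excludes an aPTT above twice normal only in combination with AST and/or ALT above 500.

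**Step 4: exactly 16 s, if the relative limb is used alone.** Row 4 ends at 15 s above target and row 5 starts beyond 16 s, so exactly 16 s above is unassigned (141 s at b = 50). Merely reversing the sign in row 1 would leave the same gap below (59 s at b = 50). The seconds limb has no such gap: 96 − 80 = 16 s above falls in row 5.

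**Step 5: both limbs applied to one patient.** The table lists values that are at goal by one window and off goal by the other.

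| Assumed baseline | Ratio goal | Values at goal by one window only | Instructions |
|---|---|---|---|
| 32 s | 48-80 s | 48-59 (12) | none and +0.02 |
| 36 s | 54-90 s | 54-59 (6) | none and +0.02 |
| | | 81-90 (10) | none and −0.02 |
| 40 s | 60-100 s | 81-95 (15) | none and −0.02 |
| | | 96-100 (5) | none and −0.04 |
| 50 s | 75-125 s | 60-74 (15) | none and +0.02 (also +0.04 from row 1 as printed) |
| | | 81-95 (15) | none and −0.02 |
| | | 96-125 (30) | none and −0.04 |

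The totals are 12, 16, 20 and 60. Further values are off goal by both windows but get steps of different size. With row 1 corrected, all values with two instructions number:

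- 32 s: 12 + 12 (33-44 s) = 24
- 36 s: 16 + 6 (39-44 s) + 10 (96-105 s) = 32
- 40 s: 20 + 15 (101-115 s) = 35
- 50 s: 60 + 15 (45-59 s) + 15 (126-140 s) = 90

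**Step 6: size of the disputed step in row 1.** The dispute is 0.04 − 0.02 = 0.02 mg/kg/hr. Against the starting rates this is 0.02/0.15 = 13%, 0.02/0.08 = 25%, 0.02/0.05 = 40% and 0.02/0.02 = 100% (dialysis).

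**The case against.** Clinicians would probably read row 1 as intended. Its own seconds limb has the right cut, row 5 mirrors it with the correct sign, and the literal reading makes no pharmacological sense. This stands as to likely practice, and it is why the slip is described as a sign error. It does not justify leaving a wrong threshold in a dosing table.

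The sentence above the table can fairly be read as giving the seconds limb to patients with a normal aPTT and the relative limb to the rest. That reading removes every double instruction in Step 5. It stands as the probable intent, but it is not stated, and normal is undefined.

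The faults do not all arise together. The 16 s gaps need the relative limb to be used alone, and the Step 5 conflicts need both limbs to be used. They should not be added up.

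A reader might infer from the percentages in Step 6 that patients face a dose error of up to 100%. The documents do not support that. The undisputed row 2 step is also 0.02 mg/kg/hr, so the percentages describe the plan's step size against low starting rates. They do not measure harm. The plan also has safeguards: "Bivalirudin dose change: 2 hours after change" for the aPTT, hourly ACT, and the statement that "bivalirudin also has a short half-life of 25 minutes".

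**Conclusion.** The point holds as a minor to should-fix wording correction of a dosing rule. Row 1 is wrong as printed, which matters mainly for patients with a baseline above about 40.7 s. For a patient titrated only on 60-80 s, the seconds limbs are complete and do not overlap. The mismatch between 60-80 s and 1.5-2.5 times baseline is arithmetic and rests on no assumption. The counts of conflicting values rest on assumed baselines and on both limbs being applied to one patient.

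A reader might go further and infer that the table is unusable, that patients will be misdosed, or that the primary comparison is biased. None of these follows. The documents give no distribution of baseline or on-treatment aPTT, so neither the number affected among the 15 bivalirudin patients nor any effect on time at goal can be estimated.

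**What to change.** 1. Reword row 1 as *below 45 s, or at least 16 s below the lower target limit*, and row 5 as *above 95 s, or at least 16 s above the upper target limit*.
2. State that each patient has one target window, fixed from the pre-cannulation aPTT before bivalirudin starts and rounded to whole seconds, and that only the matching limb of each row is used. The plan's own text points to 60-80 s for a normal aPTT and 1.5-2.5 times baseline otherwise. The clinical team should define normal and confirm the choice.
3. State in section 14 that bivalirudin time at goal is scored with that same window.

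The cost is a short amendment and brief staff retraining, with no added patients. Two consequences of item 2 need clinical acceptance:

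- **Departure from the ratio goal.** The 60-80 s window departs from 1.5-2.5 times baseline below 32 s or above 40 s. At 30 s, 76-80 s exceeds 2.5 × 30 = 75 s. At 45 s, 60-67 s is below 1.5 × 45 = 67.5 s.
- **A narrower window.** It is 80 − 60 = 20 s wide, against 80 − 48 = 32 s and 100 − 60 = 40 s for the ratio goals at baselines of 32 and 40 s. It may therefore bring more dose changes and 2-hour rechecks than the ratio window would.

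### At the dialysis starting rate of 0.02 mg/kg/hr, the fixed bivalirudin titration steps order a full stop or a negative rate, and the protocol has no hold rule

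*Combined protocol and SAP*

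**What the plan says.** Section 4, Bivalirudin group, contains two tables.

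- **Titration table.** It moves the infusion by a fixed amount per aPTT band. Above 95 s the order is "Decrease by 0.04 mg/kg/hr". At 81-95 s it is "Decrease by 0.02 mg/kg/hr". In the goal row, "60-80 seconds or 1.5-2.5 times baseline aPTT", the dose is left alone. At 45-59 s the rate rises by 0.02 mg/kg/hr, and below 45 s by 0.04. Each band also has a version relative to the patient's own target; the values in seconds apply when the baseline aPTT is normal.
- **Renal table.** "For patients with renal insufficiency or failure, the initial bivalirudin dose will be adjusted based on creatinine clearance according to the nomogram below". The starting rates are 0.15, 0.08 and 0.05 mg/kg/hr by creatinine clearance, and 0.02 for dialysis dependence. The titration steps are not adjusted.

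The aPTT schedule is "Bivalirudin dose change: 2 hours after change" and "Once achieved goal: every 6 hours". On heparin, the same section says: "Once consent is obtained, the patients will be immediately transitioned from UFH to bivalirudin".

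Patients on dialysis are expected. Section 1 plans to describe the median dose in renal insufficiency and renal failure, and no criterion in section 7 excludes them.

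**The concern.** The starting rates span a 7.5-fold range (0.15 / 0.02), but the steps are the same for everyone. A cut that is modest at 0.15 removes the whole infusion, or more, at 0.02. Heparin has by then been replaced, so a stop leaves the patient with no anticoagulant infusion ordered. Section 2 describes anticoagulation as essential to avoid catastrophic clotting of the circuit. At stake is whether bedside staff can carry out the order as written, and whether they know when and at what rate to resume.

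**Working it through.** **Inputs.** All come from section 4, Bivalirudin group: starting rates 0.15, 0.08, 0.05 and 0.02 mg/kg/hr; downward steps 0.02 and 0.04; recheck 2 h after a change; 6-hourly aPTT once at goal. The half-life of 25 min is from section 2, and the 20% renal clearance is from section 3. The plan gives no figure of its own to reproduce.

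**Step 1: the first downward order.** New rate = current rate - step.

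| Starting rate | After -0.02 (81-95 s) | After -0.04 (above 95 s) | Consecutive cuts to zero or below (small / large) |
|---|---|---|---|
| 0.15 | 0.13 | 0.11 | 8 / 4 |
| 0.08 | 0.06 | 0.04 | 4 / 2 |
| 0.05 | 0.03 | 0.01 | 3 / 2 |
| 0.02 | 0 | -0.02 | 1 / 1 |

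The large-step paths are 0.05 → 0.01 → -0.03, 0.08 → 0.04 → 0, and 0.15 → 0.11 → 0.07 → 0.03 → -0.01. Only the dialysis row reaches zero or below on the first cut. As a share of the starting rate, the small step is 0.02/0.15 = 13% in a patient with normal renal function and 0.02/0.02 = 100% in a dialysis patient.

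**Step 2: what the table orders after a stop.** Take the rate as 0 and the recheck at 2 h.

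- Below 45 s: 0 + 0.04 = 0.04, double the rate that overshot. If the negative order is carried forward literally, -0.02 + 0.04 = 0.02.
- 45-59 s: 0 + 0.02 = 0.02.
- In goal: 0 + 0 = 0. On the at-goal schedule the next aPTT is 6 h later, which is 2 + 6 = 8 h after the stop.

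**Step 3: how plausible the in-goal branch is.** Assume linear kinetics, a fixed volume, and clearance at a fraction f of normal. The half-life is then 25/f min, and the drug left after t min is 2^(-t·f/25). Exposure at 0.02, relative to 0.15 with normal clearance, is (0.02/f)/0.15.

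| f | Basis | Relative exposure at 0.02 | Left at 2 h | Left at 8 h |
|---|---|---|---|---|
| 0.80 | only the 20% renal share is lost | 16.7% | 7.0% | negligible |
| 0.50 | assumed | 26.7% | 18.9% | 0.13% |
| 0.25 | assumed | 53.3% | 43.5% | 3.6% |
| 0.133 | 0.02/0.15, if the starting rates were meant to match exposure | 100% | 64.2% | 17.0% |

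Only f = 0.80 follows from a clearance figure in the documents. At that value exposure is low, so low first aPTTs may be more common than high ones, and little drug remains at 2 h. The in-goal branch becomes more plausible only if clearance is well below that, or if something other than bivalirudin (residual heparin, coagulopathy) raised the aPTT.

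**The case against.** The strongest reply is that an order of 0 can be carried out. Stopping the lowest starting rate when the aPTT is above goal is a defensible clinical choice, and with a short half-life a brief pause is a usual response. The table also restarts the drug once the aPTT falls below goal. Monitoring continues meanwhile: the other labs include "Every hour ACT", a clot score is done every 6 hours (section 3), and crossover and withdrawal remain open. The DSMP cited in section 11 and the hospital's own ECMO protocol, to which sections 4 and 11 defer, may contain a hold rule. Section 6 of the published exclusions aside, the hospital has also used bivalirudin in six non-ECMO patients (section 2).

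Much of this stands. A reader might infer that the plan offers no way back from a stop; that is too strong, because both below-goal rows give a restart rate. A reader might also infer that these patients would spend eight hours without anticoagulation. That needs both an in-goal recheck and a literal reading of the no-change row, and the persistence figures that favour it rest on clearance fractions the documents do not give. Nor can one say that staff have no guidance at all, since the institutional documents were not available.

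What survives is narrower. The order of -0.02 cannot be executed, the goal row makes no sense while the infusion is off, and none of the monitoring or crossover provisions sets a bivalirudin rate. The crossover criteria concern thrombosis with inadequate anticoagulation or intracardiac thrombus, not an aPTT that is too high.

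**Conclusion.** The point holds as a minor dosing-safety and executability correction. While a dialysis patient's rate is still 0.02 mg/kg/hr, a result in either decrease row orders 0 or -0.02. From 0.05 or 0.08, two consecutive results above 95 s do the same. The protocol and SAP give no hold instruction, and after a stop they order a restart only on a below-goal aPTT.

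The arithmetic needs no assumption beyond reading the tables as written. The frequency is unknown and probably low: the number of dialysis patients among the 15 in the bivalirudin arm is not given, nor is the chance of a high aPTT at 0.02. A first low result would raise the rate and remove the one-step problem. It would be tempting to infer a distorted time-at-goal comparison or a distorted median dose in renal failure, but nothing in the documents shows a material effect on either.

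**What to change.** Add one rule under the titration table, for example:

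> If the ordered decrease equals or exceeds the current rate, hold the infusion (or, for 81-95 s, halve the rate if the pump can deliver it). While held, recheck aPTT every 2 hours; the no-change row does not apply. Once aPTT is no longer above goal, restart at no more than the previous rate (for example, half of it), then resume the table at the next 2-hour aPTT.

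Cuts that can be given, such as 0.05 to 0.01, stay as written. The rule should not carry an open-ended cap on later increases: after a restart at 0.02, a cap at 0.02 would block the first increase a below-goal patient needs. After halving to 0.01, the table's steps give 0.01 + 0.02 = 0.03 or 0.01 + 0.04 = 0.05, both above the rate that overshot. If a cap is wanted, it should apply to the restart rate itself or, after halving, to the first increase only.

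Clinicians and pharmacy should set the restart rate and the lowest deliverable rate. For an assumed 3 kg infant, 0.01 mg/kg/hr is 0.03 mg/hr, which is 0.3, 0.06 or 0.006 mL/hr at assumed concentrations of 0.1, 0.5 or 5 mg/mL, so the dilution needs checking.

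The cost is a short protocol amendment, a few extra 2-hourly aPTTs while an infusion is held, and possibly a slightly longer time above goal when the rate is halved instead of stopped. No extra patients are needed.
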